8.0 SAFETY MONITORING

The intraoperative anesthetic and postoperative intensive care management of these patients will be the responsibility of the anesthesiologist or critical care physician, respectively.

Possible Adverse Events: Primary clinical concerns include the formation of methemoglobin and inhibition of platelet function. Phase I studies of sodium nitrite infusion have been completed in more than 80 normal human volunteers at the doses planned for this trial with no observed toxicity (e.g., no clinically significant increases in methemoglobin or hypotension). Nevertheless, plasma methemoglobin will be measured throughout the intraoperative and immediate postoperative periods. The study drug will be discontinued should methemoglobin levels increase to 5% or greater. Parameters related to coagulation and bleeding will be monitored per standard of care. Adverse coagulation or excessive bleeding will lead to immediate cessation of study drug. Based on our prior experience with inhaled NO (**Lang REF**), we do not anticipate increased bleeding relative to placebo and anticipate that metHb levels will remain $< 5\%$ for the duration of nitrite administration

Assessment of Level of Risk: Very low (numerous studies have established safety of nitrite infusion).

Oversight of this investigation will be provided by the PI, surgeon, and co-investigators. They will be responsible for all aspects of the conduct of the trial.

Safety oversight will be provided by the Data and Safety Monitoring Board (DSMB).

9.0 Adverse Events Reporting: This study poses minimal risk.

10.0 References:

4. XIAP overexpression in islet beta-cells enhances engraftment and minimizes hypoxia-reperfusion injury. Emamaullee J, Liston P, Korneluk RG, Shapiro AM, ...

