5.0 EXPERIMENTAL PROTOCOL

Protocol Design:

This is a single institution, randomized, placebo-controlled clinical study. There will be 3 cohorts: control group, pre-isolation nitrite infusion, and a post-isolation (reinfusion) cohort.

After induction of general anesthesia with propofol (1-1.5 mg/Kg), tracheal intubation, the establishment of central venous access, invasive monitors and maintenance anesthesia with sevoflurane (1-1.5 minimum alveolar concentration) in 50:50 oxygen: air, infusions will be administered based on the randomization assignment.

I. Control Group A placebo (saline infusion) will be administered during the pre-isolation phase and during the reinfusion phase.

II. Pre-Isolation Infusion Group

[figure not shown]

Figure 1: Pre-isolation group schematic: Sodium nitrite will be initiated (pre-isolation infusion group) during the pre-isolation phase. Saline will be administered during the reperfusion period.

III. Post-Isolation (Reinfusion) Group

[figure not shown]

Figure 2: Reinfusion group schematic: Saline will be administered during the pre-isolation period. Sodium nitrite infusion will be initiated just prior to the reinfusion.

For all 3 groups:

Intraoperative arterial and venous blood samples (BS) will be drawn immediately prior to initiation of the infusion (BS1), 5 min prior to infusion of Islet Cells (BS2), 20 min after infusion of Islet Cells (BS3), and 40 min after infusion of Islet Cells (BS4).

Postoperative blood samples will be obtained 24, 48, 72 and 96 hours after the completion of surgery.

Results of routine lab work performed at the routine 3 month follow-up visit will be collected.

Procedure for Sample collection (email from [name] 6/28/16) – to be performed by lab tech in BMR

- 1) *Transferring blood to Eppendorf tubes,*
- 2) *Centrifuging (using a table top min-fuge which we can provide),*
- 3) *Transferring plasma to 4 other vials (1 containing a pre-made solution, which we can provide) and flash freezing all vials in liquid N₂*
- 4) *Taking some of the red cell pellet and adding to vials (containing pre-made solution that we can provide) and flash freezing all vials in liquid N₂*
- 5) *All samples need to be stored at -80C.*

Primary Endpoints:

- Markers of pancreatic function:
 - Blood glucose levels
 - HbA1c levels pre-operatively and at the 3 month post-operative visit
 - Exogenous insulin use
 - Measured from blood samples 24, 48, 72, 96 hours post op & at 3 months post op

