- Decrease in reperfusion injury
- Incidence of diabetes post-operatively

Intraoperative blood samples will be analyzed for serum and methemoglobin levels and biochemical markers of oxidative and nitrosative stress, including plasma and hepatic 3-nitrotyrosine, oxidized lipids (isoprostanes, 8-epi-PGF₂α), protein carbonyls and the NO-metabolites, nitrite, nitrate, S-nitrosothiols, C-N-nitroso compounds and heme nitrosyls. If the above processing is not part of the costs, and assuming 30 patients, each with 6 blood draws then running assays for plasma and red cell NOx, C-peptide levels, circulating pro-inflammatory chemokines/cytokines and perform immunophenotyping of monocytes and neutrophils by flow cytometry and mRNA accumulation.

	Sample Name	Blood Glucose	HbA1c	Insulin level exogenous	RF	C-peptide	Circ pro-inflammatory chemokine / cytokines	Immunophenotyping monocytes and neutrophils	mRNA				
Intraoperative													
Prior to infusion	BS1	X	X			X	X	X	X				
5 min prior to Islet cell infusion	BS2	X											
20 mins after infusion of Islet cells	BS3	X											
40 mins after infusion of Islet cells	BS4	X											
Post-op													
24 hours	BS5	X		X		X	X	X	X				
48 hours	BS6	X		X		X	X	X	X				
72 hours	BS7	X		X		X	X	X	X				
96 hours	BS8	X		X		X	X	X	X				
Follow up													
Clinic visit 3 months post-op	BS9	X	X	X		X	X	X	X				

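### Section 8.0 names plasma as the specimen behind the 5% methemoglobin stopping limit, and no section states a whole-blood reading, denominator, assay or reading times

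*Combined protocol and SAP*

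**What the plan says.** Section 8.0 (Safety Monitoring) lists methemoglobin formation first among the clinical concerns and then gives the measurement: "Nevertheless, plasma methemoglobin will be measured throughout the intraoperative and immediate postoperative periods". The stopping sentence follows directly: "The study drug will be discontinued should methemoglobin levels increase to 5% or greater". Later in the paragraph the investigators "anticipate that metHb levels will remain" below that same figure while nitrite is given.

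Section 5.0 (Experimental Protocol) returns to the measurement once: "Intraoperative blood samples will be analyzed for serum and methemoglobin levels", followed by a list of oxidative-stress and NO-metabolite assays. It schedules four intraoperative draws of arterial and venous blood (BS1 to BS4), then samples from 24 hours after surgery. The handling steps centrifuge the blood and divide it. Plasma goes one way ("Transferring plasma to 4 other vials (1 containing a pre-made solution, which we can provide) and flash freezing all vials"), and part of the cells goes another ("Taking some of the red cell pellet and adding to vials"). All vials are flash frozen and stored at -80C.

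Section 6.0 (Experimental Techniques) is marked as not applicable, so no assay is described there.

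**The concern.** The limit is a percentage, and a percentage needs a denominator. For methemoglobin the usual denominator is total hemoglobin, which is held in the red cells; plasma normally contains only a trace. That is general knowledge, since the documents do not define the percentage. On an ordinary reading, the levels in the stopping sentence are those measured in the sentence before it, and that sentence names plasma.

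This is the only safety limit in the plan with a number attached; the bleeding criterion in the same paragraph has none. It also covers the first-named risk of the study drug. Someone following the text literally would apply the limit to a specimen that says little about the patient's circulating hemoglobin. A reader of the trial's safety results could not tell what a reported percentage refers to, or whether it was available in time to be acted on.

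**Working it through.** The 5% figure is set by the investigators and not derived from other inputs, so there is nothing to reproduce. The check sets the relevant sentences side by side and then asks how much the specimen word could matter.

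**Step 1: what each section fixes about the measurement.**

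| Place | Specimen | Denominator | Assay | When read |
|---|---|---|---|---|
| 8.0, measurement sentence | plasma | not stated | not stated | during surgery and soon after, no times |
| 8.0, stopping sentence | not restated | not stated (a percentage) | not stated | not stated |
| 8.0, expected level | not restated | not stated (a percentage) | not stated | during nitrite administration |
| 5.0, intraoperative assays | blood samples; the word serum has no analyte after it | not stated | not stated | not stated |
| 5.0, handling steps | plasma and red-cell pellet, both frozen | not applicable | not stated | not stated |
| 6.0 | none | none | none | none |

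The only specimen attached to methemoglobin in the safety section is plasma. Section 5.0 speaks of blood samples and joins serum and methemoglobin with a conjunction, so it does not call methemoglobin a serum measure. It gives no unit or method either. The sampling table shows no methemoglobin column as extracted, but it may be broken, and nothing here rests on it.

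**Step 2: timing.** BS1 is taken before the infusion starts, BS2 5 minutes before islet infusion, and BS3 and BS4 20 and 40 minutes after it. The next sample is at 24 hours. Only three of the four intraoperative draws (4 - 1 = 3) can follow the start of the infusion. If nitrite in the pre-isolation arm ends with the pre-isolation phase, BS1 comes before it and BS2 after it, so no scheduled draw falls while nitrite is running in that arm. The schedule alone therefore does not clearly cover the period named in Section 8.0. Separate clinical blood draws may cover it, but the plan does not say so.

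**Step 3: how far a plasma value could be from 5%.** The documents give no hemoglobin values. Assume total hemoglobin of 10-15 g/dL (10,000-15,000 mg/dL) and free plasma hemoglobin of 1-50 mg/dL.

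Share of total hemoglobin carried in plasma = free plasma hemoglobin / total hemoglobin

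- Low end: 1 / 15,000 = 0.0067%
- High end: 50 / 10,000 = 0.5%

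Both overstate the share, because plasma is only part of the blood volume. Even if all the plasma hemoglobin were oxidized, it would not approach 5% of total hemoglobin. At 10 g/dL that would take 0.05 × 10,000 = 500 mg/dL in plasma, ten times the top of the assumed range. If the denominator were plasma hemoglobin instead, the value could lie anywhere from 0 to 100% of a trace amount. The plan states neither denominator, so these are alternatives and should not be combined.

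**The case against.** The strongest reply is that one adjective is being made to carry too much. The stopping sentence and the expected-level sentence say only methemoglobin or metHb. Section 5.0 names blood as the specimen. Whole arterial and venous blood is drawn, and part of the red-cell pellet is kept. The handling steps are laboratory instructions that nothing ties to the safety reading; they would suit the NO-metabolite and cytokine work equally well. The site may simply intend an ordinary blood methemoglobin reading and have worded it loosely.

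Much of this stands. A reader might infer that the rule cannot operate at all, or that the expectation of staying below 5% would be met by construction. The documents support neither. Suitable blood is collected, the rule does not repeat the word plasma, and the by-construction argument needs both a literal plasma assay and a total-hemoglobin denominator, which no section describes. The arithmetic uses assumed values. It shows that plasma holds little hemoglobin, not that the trial would measure it there.

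Loose wording does not dispose of the point, however. The one specimen the safety section names is the wrong one for a percentage of total hemoglobin, and no other section states a whole-blood reading, a denominator or an assay. The handling steps are no evidence of a plasma-only plan, but they also supply no reading on fresh blood.

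**Conclusion.** The concern holds in a limited form. Section 8.0 attaches a wrong specimen word to the plan's only numeric safety limit. Read literally, a plasma value does not inform a limit set as a percentage of hemoglobin. Section 5.0 is garbled on the same measurement, and the only handling it describes ends in frozen storage, with no reading described while the infusion runs. Specimen, denominator, assay and reading times are each inconsistent or unstated.

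The conclusion rests on the usual meaning of a methemoglobin percentage, which the documents do not define. The size (at most about 0.007% to 0.5% of total hemoglobin in plasma) is illustrative and rests on the assumed ranges. Nothing here shows that the trial would miss methemoglobinemia or stop drug wrongly in practice. It is a correction that should be made, because it concerns an operative safety rule and costs little. No view is taken on the 5% limit.

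**What to change.** Reconcile Sections 5.0 and 8.0 so that they describe one measurement:

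- In Section 8.0, replace plasma methemoglobin with methemoglobin in whole blood, expressed as a percentage of total hemoglobin and read on fresh, unseparated blood during the infusion.
- State the assay and the reading times, and how the result reaches the operating team. Say whether the readings use draws BS1 to BS4 or separate clinical samples, so that the period named in Section 8.0 is covered in each arm.
- In Section 5.0, clarify what the word serum refers to. An analyte may be missing after it, so it should not simply be overwritten. State that the centrifuging and freezing steps apply to the research assays, if that is what is meant.
- Leave the threshold and the decision to stop study drug as the investigators set them.

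The cost is a few sentences and a few readings during surgery. This assumes that the site's blood-gas analyzer reports methemoglobin and that the draws cover the stated period. The documents confirm neither; if the second fails, some further sampling would be needed.

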7.0 STATISTICAL CONSIDERATIONS

Primary Study Variables include: Demographics (age, gender, pre-operative weight, pre-operative BMI,

General Data Analysis: All anthropometric data will be compared using unpaired Student's t-test. Length of stay data will be compared using Cox proportional hazard

analysis. All other data will be compared using one-way repeated measures ANOVA with post-hoc analysis by unpaired Student's t-test or Chi Square analysis as appropriated. For all comparisons, a value of $p < 0.05$ will be considered significant.

This is a pilot study. We plan to enroll 10 patients in each of the 3 arms of this study (total N=30).

Study Population Availability: Approximately 8-10 patients present to UAB for this procedure annually. Potential study subjects will be identified by [name] and his clinic team.

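### Section 9.0 gives a risk rating where an adverse-event procedure belongs, and the visible text has no adverse-event collection or by-arm adverse-event summary

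*Combined protocol and SAP*

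**What the plan says.** Section 9.0 reads, in full, "9.0 Adverse Events Reporting: This study poses minimal risk"; the reference list follows directly. The risk assessment in section 8.0 rests on the statement that "numerous studies have established safety of nitrite infusion".

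Section 8.0 does contain safety provisions:

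- Methemoglobin is measured during surgery and in the immediate postoperative period, and study drug stops at 5% or more. Section 5.0 also lists it as an assay: "Intraoperative blood samples will be analyzed for serum and methemoglobin levels".
- "Parameters related to coagulation and bleeding will be monitored per standard of care", and study drug stops for abnormal coagulation or excessive bleeding.
- A board is named: "Safety oversight will be provided by the Data and Safety Monitoring Board (DSMB"). Its inputs and meeting schedule are not described.

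Hypotension appears once, as something not seen in earlier volunteer studies: "no clinically significant increases in methemoglobin or hypotension".

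In section 7.0, "Length of stay data will be compared using Cox proportional hazard" analysis, and then "All other data will be compared using one-way repeated measures ANOVA", followed by t-tests or Chi Square, with p < 0.05 applied to every comparison. No adverse-event analysis is named.

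**The concern.** A risk rating does not say what is to be recorded, over what period, by whom or for whom. Followed as written, the trial would give an intraoperative study drug against a concurrent saline arm without systematic adverse-event data.

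The rating leans on evidence from a different setting. The hypotension statement comes from healthy volunteers. Here nitrite is infused under general anesthesia, maintained with sevoflurane, during removal of the pancreas and islet infusion. Section 8.0 also cites the group's own experience with inhaled nitric oxide, but applies it to bleeding and methemoglobin.

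Section 1.0 calls this a pilot that may lead to further investigations. Those studies would want tolerability data against placebo. Events that nobody asked about over 3 months cannot be reliably recovered at the analysis stage.

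**Working it through.** The point concerns missing content, so the main check is a reading of each place where adverse-event collection or analysis could stand.

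| Place | What it provides | Adverse events collected or summarised by arm? |
|---|---|---|
| 5.0, endpoints | Glucose, HbA1c, exogenous insulin, reperfusion injury, incidence of diabetes | No |
| 5.0, sampling text and table | Blood assays, including methemoglobin intraoperatively | No; the table schedules assays only |
| 5.0, 3-month visit | Routine labs, exogenous insulin use, C-peptide and other assays | No |
| 7.0 | Length of stay; general sentence for all other data | No; it analyses data once they exist |
| 8.0 | Methemoglobin and bleeding rules, DSMB | Not beyond these items |
| 9.0 | Risk rating | No |

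Methemoglobin values are study data and would fall under the general ANOVA sentence. The gap is therefore adverse events, not every safety measurement.

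**What capture could show.** The plan's sample size is 3 arms × 10 = 30, which agrees with its stated total. Nitrite is assigned to 2 × 10 = 20 patients, in different phases of surgery. The plan gives no adverse-event rates.

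*Zero occurrences of a given event, one-sided 95% upper limit:* 1 − 0.05^(1/n).

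- n = 10: 1 − 0.05^(1/10) = 25.9%
- n = 20: 1 − 0.05^(1/20) = 13.9%

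*Chance of seeing a given event at least once:* 1 − (1 − p)^n, with p assumed.

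| Assumed true rate on nitrite | n = 10 | n = 20 |
|---|---|---|
| 5% | 1 − 0.95^10 = 40% | 1 − 0.95^20 = 64% |
| 10% | 1 − 0.90^10 = 65% | 1 − 0.90^20 = 88% |
| 20% | 1 − 0.80^10 = 89% | 1 − 0.80^20 = 99% |

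A common harm would very probably occur in this trial, but it enters the record only if someone records it. These figures describe how precise the remedy would be; they do not measure the defect. They apply to one defined event type, not to any adverse event after major surgery.

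**The case against.** The strongest reply is that the main nitrite risks are already covered. Section 8.0 names methemoglobin and platelet inhibition as its primary concerns and gives each a stopping rule. The volunteer data are at the doses planned here, a DSMB is in place, and 30 patients are too few to compare rates.

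Much of that stands, and it rules out several stronger readings that a reader might infer:

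- *That the trial has no safety monitoring.* The rules in section 8.0 contradict this.
- *That blood pressure and vasopressor use will not be captured.* The visible text does not mention recording them, but the variable list in section 7.0 breaks off after BMI. The visible lists are also not exhaustive: length of stay is analysed yet appears in none of them. Blood pressure is presumably observed through the invasive monitors, and both items can be taken from the chart later.
- *That the plan treats hypotension as an expected harm.* It mentions it only as not observed. The background in section 2.3 describes inhaled nitric oxide as having little effect on systemic pressure, though by another route.
- *That the DSMB will receive no safety data.* The documents do not say what it receives, and a charter outside them may.
- *That 30 patients could detect a blood-pressure effect.* No such claim is made.

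The reply does not reach adverse-event ascertainment. A board can review only what has been collected, and the general analysis sentence causes nothing to be collected. Small numbers argue for description with intervals, not for leaving events unrecorded.

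**Conclusion.** The point holds for adverse events: the visible text has no procedure for collecting them as study data and no by-arm summary of them. This is more than missing detail, because the loss is largely permanent once follow-up ends. It should be corrected.

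No figure in the plan changes, and no sample-size change is needed. With 10 per arm the resulting table would be descriptive and imprecise, with zero-event upper limits of 25.9% for one arm and 13.9% for both nitrite arms pooled. Pooling assumes that the two infusion phases may be read together for the event in question.

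The conclusion rests on the visible protocol and SAP text. A DSMB charter or case report form outside it could already cover part of the gap.

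**What to change.** Replace the section 9.0 sentence with a short procedure:

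1. Collect adverse events and serious adverse events in all 30 patients, from the start of infusion through the existing 3-month visit. State definitions, grading, relation to study drug, and reporting timelines and recipients.
2. Record any early stopping of study drug, with the reason.
3. Report a table by arm, as counts with confidence intervals, to the DSMB and in the final report. Exempt it from the p < 0.05 rule in section 7.0.

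Lowest blood pressure, vasopressor use, peak methemoglobin and blood products are suggested items, to be extracted from existing monitoring and charts; the investigators can adjust the list. If lowest pressure is used, read it together with vasopressor use, since falling pressure is treated. Fix its time window too: section 4.2 gives 100 mL at 10 mL/min, which is 100/10 = 10 minutes, yet also has the infusion run for the whole operation. No new stopping threshold is proposed.

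The cost is modest: protocol wording, chart extraction for 30 patients, and a brief adverse-event review at the 3-month visit, which already collects labs and insulin use. No visit or procedure is added.
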